13 STATISTICAL CONSIDERATIONS

13.1 Study Design

This is a two-arm randomized Phase II trial. All the enrolled patients with resectable pancreatic cancer will undergo surgery. Patients will be 1:1 randomized to one of two treatments: neoadjuvant CDX-1140 vs. CDX-301 plus CDX-1140.

13.2 Sample Size Calculation

The primary endpoint is intratumoral conventional dendritic cells (cDCs) at surgery. The sample size calculation is based on the primary endpoint only. Our pilot data in animal models showed that the mean and standard deviation of the number of intratumoral cDCs per gram of tissue in CD40 agonist IgGs was 44726 with a standard deviation of 37895, and for mice treated with CDX-301 plus CD40 agonist, the mean cDCs per gram of tissue was 2716742 with a standard deviation of 1322448. Assuming a similar therapeutic effect on cDCs and similar distribution among samples, 12 patients per arm will have at least 99.9% power to detect the intratumoral cDCs difference as measured by CyTOF between two arms using a two-sided two-group T-test at the type I error of 5%. We plan to enroll 12 patients evaluable for the primary objective per arm for a total of 24 evaluable patients. An interim analysis can be performed at 5 patients per arm or greater; 5 patients per arm will have >80% power to detect changes in cDCs.

13.3 Accrual

We perform surgery in 80-110 patients per year at Washington University with similar characteristics and estimate approximately 30-40 patients/year may be eligible for and will participate in this trial. We anticipate enrollment of approximately 1-3 patients per month.

13.4 Statistical Analyses

13.4.1 Patient Disposition

The number of patients discontinued, the reasons for discontinuation, and the amount of therapy administered will be summarized by patient and by reason for discontinuation by arm.

13.4.2 Protocol Deviations

All significant deviations will be summarized by patient and by type of deviation.

13.4.3 Demographics and Baseline Characteristics

Subject demographic and clinical characteristics will be summarized to characterize the population. Descriptive summaries will include means, standard deviations, medians, ranges for continuous variables and frequency and percentage for categorical variables. They are presented by total and each arm, respectively.

13.4.4 Endpoint Analysis

The primary endpoint is intratumoral cDCs in surgical tissues. Conventional dendritic cells are defined by the lack of expression of CD3, CD19, CD20, CD16, CD56, and the expression of CD45, CD11c, MHCII high and either CD1c or CD141. Kruskal-Wallis test will be used to compare the difference between two

arms.

Exploratory endpoints include global immune profiling by CyTOF, single cell RNASeq analysis, and histologic assessments. Kruskal-Wallis test will be used to compare the difference on T cell and cDC number and phenotype between two arms.

Additional exploratory endpoints include local control rate, distant metastasis-free survival (DMFS), overall survival (OS), and margin negative resection rate. Proportions of local control and margin negative resection for all treated patients and their associated 95% confidence intervals will be calculated assuming a binomial distribution. Chi-square or Fisher's exact test will be used to compare the difference between two arms.

OS is defined as the time from the date of treatment to the date of death, censored at the last follow-up otherwise. DMFS is defined as the time from treatment to the date of distant metastasis or death, whichever occurs first. The alive patients without distant metastasis is censored at the last follow-up. The Kaplan-Meier method will be used to calculate the probability of OS and DMFS. The log-rank test will be considered to compare the difference of OS and DMFS between two arms.

Data on the toxicity in each arm will be collected for each subject, including frequency, type, and severity of adverse events. All analyses will be conducted using SAS (SAS Institute, Cary, NC) at the two-sided 5% significance level.

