1.3 Study Design

1.3.1 Overall Design

Hypothesis: The combination of CDX-301 and CDX-1140 will work synergistically to improve anti-tumor immunity, both within tumor tissue and systemically. Specifically, we believe these two agents will combine to increase cDCs and T cells within tumor tissues.

[figure not shown]
Clinical trial design: The trial is a phase II, single institution, open-label, randomized trial treating patients with surgically resectable pancreas cancer. Patients will be accrued upon designation of surgical resectability by our tumor board. Patients will be randomized to receive either CDX-1140 alone or CDX-310 plus CDX-1140 prior to surgery. Patients will receive a single 7-day cycle of treatment followed by surgery 7-12 days after cycle completion. Surgical resection tissue will be accessed for endpoint and compared historical controls.

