4.3 Assignment of UPN

Each patient will be identified with a unique patient number (UPN) for this study. All data will be recorded with this identification number on the appropriate CRFs.

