4.6 Measures to Minimize Bias: Randomization

Consenting and eligible patients will be randomized on a 1:1 basis to receive CDX-1140 followed by surgery or CDX-301 + CDX-1140 followed by surgery until 12 patients evaluable for the primary objective have been randomized to each arm. The randomization table will be generated by the statistician using a statistical software and will be uploaded to REDCap to randomize patients.

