9.4 Specimen Analysis

First, we will assess the impact of CDX-1140 compared to CDX-301/CDX-1140 on multiple parameters of PDAC local and systemic tumor immunity. Second, we expect diverse objective responses to therapy; blood and PDAC tissues parameters can be correlated with patient outcomes to identify the biological parameters that indicate therapeutic benefit.

Our tissue collections will include pre- treatment and time of surgery blood and sera, as well as tumor tissue collected at the time of surgery. Tissue collection will be mandatory for all patients. Tumor tissues will be divided into cryopreserved, formalin-fixed paraffinembedded (FFPE), and flow cytometry/CyTOF samples. We will directly assess how notreatment vs CDX-1140 vs CDX-301/CDX-1140 alters immune cell tumor infiltration using high-density flow cytometry and CyTOF. We optimized two 14-parameter flow cytometry protocols to assess T-cell infiltration, activation, and exhaustion, and myeloid cell and DC infiltration and two 35 parameter CyTOF panel (see **Figure**). This will be complemented by Single Cell RNA sequencing when tissue it sufficient. Conventional dendritic cells are defined by the lack of expression of CD3, CD19, CD20, CD16, CD56, and the expression of CD45, CD11c, MHCII high and either CD1c or CD141.

On archival FFPE tissues we will complement flow cytometry with multiplex IHC on FFPE tissue. We optimized several multiplex IHC panels using the PerkinElmer OPAL system. These panels can identify changes in T-cell infiltration and proliferation (e.g., CD3⁺/CD8⁺/Ki67⁺) and proximity to tumor cells (CK19). For imaging and deconvolution we will capture images and conduct quantitative analysis using HALO pattern recognition software.

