We will analyze blood leukocyte populations using two optimized 36-parameter CyTOF panels designed for adaptive and innate immune cells, respectively. We will focus on evidence of increased T-cell activation corresponding with tumor reactivity (similar to results from human checkpoint studies^{43, 44}). This will include analyses of T-cell proliferation (Ki67), lineage transcription factors (e.g., GATA3, T-bet, Eomes), effector function (Granzyme B, perforin), memory status (e.g., KLRG1, CD28, CD127), exhaustion/checkpoint marker expression (e.g., 41BB, LAG3, TCF1 and SLMF6). We will perform unguided analysis of this CyTOF data using PhenoGraph and X-Shift to identify uniquely changing T-cell subsets, and Citirs to determine potential biomarkers of treatment response.

Α	Human CyTOF T Cell Pannel				
	Marker	Metal	Marker	Metal	
	CD45	089Y	CCR7	159Tb	
	open	115In	CD39	160Gd	
	CCR6	141Pr	Tbet	161Dy	
	CD19	142Nd	FoxP3	162Dy	
	ICOS	143Nd	BTLA	163Dy	
	CD38	144Nd	GITR	164Dy	
	CD4	145Nd	CD16	165Ho	
	IgD	146Nd	CD24	166Er	
	RORgt	147Sm	Gata3	167Er	
	PD-L1	148Nd	CD8	168Er	
	open	149Sm	IL-2R	169Tm	
	CD27	150Nd	CD3	170Er	
	CD14	151Eu	GranzymeB	171Yb	
	CTLA-4	152Sm	Ki67	172Yb	
	TIGIT	153Eu	CXCR4	173Yb	
	TIM-3	154Sm	PD-1	174Yb	
	CD45RA	155Gd	Perforin	175Lu	
	CXCR3	156Gd	NCAM	176Yb	
	CCR4	158Gd	CD11b	209Bi	
B PhenoGraph on α/β T Cells PDAC Tissues TH CTLs TReg					
TSNE-1 Figure. (A) T-cell CyTOF panel (B) CyTOF data from human PDAC					

subsets by PhenoGraph.

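### Open-label trial: nothing in the plan hides the arm from whoever gates the primary cDC count or fixes the gate in advance, so knowledge of the arm could bias it

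*Combined protocol and SAP*

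**What the plan says.** - Section 1.3.1 describes an "open-label, randomized trial treating patients with surgically resectable pancreas cancer".
- Section 4.6 is titled "Measures to Minimize Bias: Randomization". It gives 1:1 allocation and its mechanics: "The randomization table will be generated by the statistician using a statistical software", then loaded into REDCap. No other bias measure appears there.
- Section 13.4.4: "The primary endpoint is intratumoral cDCs in surgical tissues". The cells must lack CD3, CD19, CD20, CD16 and CD56 and show "the expression of CD45, CD11c, MHCII high and either CD1c or CD141". Section 9.4 gives the same phenotype ("CD11c, MHCII high and either CD1c or CD141"). Neither place gives a threshold, a gating control, a template or a second read.
- Section 13.2 says the count is measured by CyTOF. It plans 12 evaluable patients per arm and permits an interim analysis once there are 5 or more per arm.
- Section 9.4 on automated analysis: "We will perform unguided analysis of this CyTOF data using PhenoGraph and X-Shift to identify uniquely changing T-cell subsets". This follows the description of the blood leukocyte panels. HALO image analysis is assigned to multiplex IHC.
- Section 4.3 on coding: "Each patient will be identified with a unique patient number (UPN) for this study".

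**The concern.** Randomisation makes the arms comparable when treatment is allocated. It does nothing for an outcome measured later by someone who may know the allocation. A cell count by cytometry depends on where the boundaries are drawn, and a marker required to be high, with no value attached, leaves that boundary to be chosen. Fresh tumour goes to one research laboratory as each patient has surgery (9.1), so samples may be processed over the whole accrual period and on both sides of an interim look.

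The documents expect the combination to do better. The synopsis hypothesis says so, and section 1.2.6 reports strong synergy in mice. If the arm is known when gates are set, a small systematic difference in the cut could enter the only primary comparison, and no later analysis of the counts could separate it from a drug effect.

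**Working it through.** **1. Does any stated safeguard cover the primary readout?**
- Randomisation table in REDCap (4.6): governs allocation, not measurement.
- Unsupervised clustering (9.4): described for blood CyTOF and T-cell subsets, not for the tumour cDC count.
- HALO (9.4): for multiplex IHC.
- Patient number (4.3): identifies the patient on case report forms and is not said to conceal the arm.
- Specimen sections (9.1 to 9.4) and statistics sections (13.1 to 13.4.4): silent on masking of the laboratory or the statistician.

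None covers it.

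**2. The plan's own power figure, for context.** Mouse inputs from 13.2: mean 44,726 (SD 37,895) on CD40 agonist; mean 2,716,742 (SD 1,322,448) on the combination.
- Ratio of means: 2,716,742 / 44,726 = 60.7.
- Difference: 2,672,016. Pooled SD: √[(37,895² + 1,322,448²)/2] = 935,496. Standardised effect: 2.86.
- 12 per arm, two-sided 5%: noncentrality 2.86 × √(12/2) = 7.0 on 22 df, power above 99.99% (stated: at least 99.9%).
- 5 per arm: 97.6% by the equal-variance t-test, 91.4% by Welch (stated: above 80%).

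The stated power reproduces. Masking changes neither sample size nor power.

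**3. Illustration of the exposure.** The shift sizes are assumptions. The spread comes from the mouse CVs: 37,895/44,726 = 0.847 and 1,322,448/2,716,742 = 0.487. With log-SD = √ln(1 + CV²), these give 0.736 and 0.461.

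Model: lognormal counts, 12 per arm, no true difference, two-group Kruskal-Wallis at 5%, with a spurious fold shift applied to one arm. Ranges run from both arms at log-SD 0.74 (lower figure) to both at 0.46 (higher figure). Giving one arm each value falls between them in every shifted scenario. Results are from 20,000 runs per setting, checked with 200,000.

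| Spurious shift | All 12 samples of one arm | Half of one arm | All 12, assumed CV 1.2 |
|---|---|---|---|
| none | about 5% | – | about 5% |
| 1.1-fold | 6–8% | 5–6% | 6% |
| 1.25-fold | 11–20% | 6–8% | 9% |
| 1.5-fold | 25–53% | 9–15% | 17% |

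**4. When does it matter?**
- Near the mouse effect: a 1.5-fold artefact working against the combination leaves 60.7/1.5 = 40-fold, and simulated power stays at about 100%. A modest shift neither creates nor hides such an effect.
- At the two-fold change that section 11 says the study is powered for: Kruskal-Wallis power with 12 per arm is about 58% (CV 0.85) to 93% (CV 0.49). A 1.5-fold artefact would make the apparent ratio 2 × 1.5 = 3.0 or 2/1.5 = 1.3, depending on its direction. That is material.

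**The case against.** The strongest reply is that the documents are silent on these points, and silence does not show a biased measurement.

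- **Arm known in the laboratory.** A reader might infer that samples arrive labelled by arm. The documents do not say so. The one tube label they describe, for the anti-drug-antibody sample in 9.3, carries patient ID, date and visit time point, without arm. What can be said is that the plan does not state whether the arm is concealed.
- **Manual gating, patient by patient.** A reader might infer this from the missing cut-off. No section says that gating is manual. It is possible under the text but not stated.
- **Existing protections.** The phenotype is fixed in advance, the panels are described as optimised, and single-cell sequencing and histology could serve as cross-checks. This is fair. But a marker list is not a threshold, the sequencing depends on sufficient tissue, and the cross-checks are exploratory and not themselves said to be masked.
- **Size.** A reader might take 25–53% as the trial's real false-positive rate. The documents give no gating-variability figure, and that range needs a 1.5-fold shift in every sample of one arm. Half-arm shifts or greater human variability give much smaller figures.
- **Planning effect.** At a 61-fold difference the point disappears. True, but that figure is from mice, section 11 names two-fold, and section 1.3.3 says the effect in human tumours is what the trial is meant to learn.

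The limits on inference and size stand. The absence of any stated protection for the primary measurement stands too.

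**Conclusion.** The point holds as a gap in protection. In an open-label trial, the only primary endpoint is a gated count with a qualitative MHCII cut. No section conceals the arm from whoever sets the gates, and none fixes the gate beforehand. It does not invalidate the design, and the documents do not show that bias has occurred or would occur.

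The size is conditional. With no true effect, false-positive rates range from barely above nominal to about half across the scenarios shown. They rest on assumed shifts, lognormal counts and mouse CVs. The gap matters if the human effect is absent or near two-fold, and not if it approaches the mouse effect. Some figures and pages are missing from the public copy, but the randomisation, laboratory and statistics sections, where masking would be expected, are present and silent. Because the remedy is cheap, it should be made.

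**What to change.** Add to sections 4.6 and 9.4:

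1. Tumour samples and cytometry files carry a study code that does not reveal the arm.
2. One written gating template for the primary count, including the MHCII cut and the controls that set it, is locked before any arm-level look. That includes the optional interim at 5 per arm.
3. Existing laboratory staff without access to allocation apply the template.
4. The statistician links codes to arms only after the counts for that look are locked. Counts locked for an interim are not re-gated afterwards.

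If samples have already been gated, stored cytometry files could be re-gated masked under the locked template.

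Cost: relabelling and a short written procedure. Sample size, power, patient procedures and treatment do not change. Two limits remain. Masking may be imperfect if dendritic-cell expansion is evident in the samples, particularly as tumour and research blood go to the same laboratory. The documents give no staffing details, so the availability of someone without allocation access is an assumption to confirm.

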5.3 Definitions of Evaluability

Patients must undergo collection of blood and tissue at the time of resection in order to be evaluable for the primary objective of determining amount of intratumor cDC. Patients who are not evaluable for the primary objective will not count towards analysis of this

objective and will be replaced. However, these patients will continue on study/in followup to be followed for toxicity and local control, DMFS, and OS regardless of whether they had resection.

All patients who receive any study treatment are evaluable for the exploratory objective of safety and tolerability. Patients are evaluated from first receiving study treatment until time of resection, or until 60 days after end of treatment if resection doesn't take place.

In order to be evaluable for the exploratory objective evaluating immunologic correlates, patients must have blood and tissue collected before and after therapy.

In order to be evaluable for the exploratory objectives of assessing local control, DMFS, and OS, patients must have received at least one dose of study treatment.

In order to be evaluable for the exploratory objective of assessing extent of resection, patient must have received at least one dose of study treatment and undergone resection.

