5.5 Women of Childbearing Potential

Women of childbearing potential (defined as women with regular menses, women with amenorrhea, women with irregular cycles, women using a contraceptive method that precludes withdrawal bleeding, and women who have had a tubal ligation) are required to have a negative serum or urine pregnancy test within 14 days prior to the first day of study treatment.

Female and male patients (along with their female partners) are required to use two forms of acceptable contraception, including one barrier method, during treatment with the investigational agents.

If a patient is suspected to be pregnant, the study agent should be immediately discontinued. In addition, a positive urine test must be confirmed by a serum pregnancy test. If it is confirmed that the patient is not pregnant, the patient may resume dosing.

If a female patient or female partner of a male patient becomes pregnant during therapy with the study agent or 3 months thereafter, the investigator must be notified in order to facilitate outcome follow-up.

5.6 **Duration of Therapy**

If at any time the constraints of this protocol are considered to be detrimental to the patient's health and/or the patient no longer wishes to continue protocol therapy, the protocol therapy should be discontinued and the reason(s) for discontinuation documented in the case report forms.

Treatment may also be discontinued early for the following reasons:

- Documented and confirmed disease progression
- Death
- Adverse event(s) that, in the judgment of the investigator, may cause severe or permanent harm or which rule out continuation of study drug
- General or specific changes in the patient's condition render the patient unable to receive further treatment in the judgment of the investigator
- Suspected pregnancy
- Serious non-compliance with the study protocol
- Lost to follow-up
- Patient withdraws consent
- Investigator removes the patient from study
- The Siteman Cancer Center decides to close the study

Patients who prematurely discontinue treatment for any reason will still be followed as indicated in the study calendar.

5.7 **Duration of Follow-up**

Patients will be followed every 6 months for 2 years or until death, whichever occurs first. Patients removed from study for unacceptable adverse events will be followed until resolution or stabilization of the adverse event.

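### Local control is analysed as a binomial proportion with no time point and no rule for death or loss, so on the default reading an arm with more deaths can show better local control

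*Combined protocol and SAP*

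**What the plan says.** Section 13.4.4 (Endpoint Analysis) treats local control and margin status together: "Proportions of local control and margin negative resection for all treated patients and their associated 95% confidence intervals" "will be calculated assuming a binomial distribution". It adds that "Chi-square or Fisher's exact test will be used to compare the difference between two arms", and all analyses are run "at the two-sided 5% significance level".

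Section 5.3 makes one dose of study treatment enough for a patient to be evaluable for local control. Patients not evaluable for the primary objective stay on study "to be followed for toxicity and local control, DMFS, and OS regardless of whether they had resection". Under Section 5.7, "Patients will be followed every 6 months for 2 years or until death, whichever occurs first". Section 5.8 records a patient who cannot be traced as withdrawn.

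Local control also appears in the synopsis, Section 2 and Section 11. None of these places defines local failure, names an assessment time, or says how to classify a patient who dies, is lost or has short follow-up without a recorded local failure. In Section 13.4.4 itself, DMFS counts death as an event, censors other event-free patients at last follow-up, and uses Kaplan-Meier and log-rank.

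**The concern.** A binomial analysis of all treated patients needs one yes or no per patient. That suits margin status, which is settled at surgery. Local failure emerges over two years, and a patient can die or be lost before it is seen. The stated method cannot represent either event.

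The natural coding is that a recorded local failure gives no and anything else gives yes. A patient who dies at month 4 without local failure then counts the same as one who is alive and free of local failure at month 24. The comparison between arms mixes local failure with mortality and observation time, and early death improves the result. With no time point, the proportion also depends on when it is computed.

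**Working it through.** **The plan's own figures.** None is stated for local control. The only power statement, at least 99.9% for cDCs at 12 per arm (Section 13.2), reproduces: the standardised difference is 2.86 and power exceeds 99.99%. It has no bearing on this point.

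**Inputs.** From the documents: follow-up of 24 months ending at death, all treated patients in the denominator, and about 12 per arm (the planned number evaluable for the primary objective). Assumed, because the documents give no rates: constant independent hazards, 40% net local failure at 24 months in every arm, and 24-month mortality of 30%, 50% or 70%.

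**Formulas.**
- Local-failure hazard: hL = −ln(1 − 0.40)/24 = 0.0213 per month.
- Death hazard: hD = −ln(1 − mortality)/24 = 0.0149, 0.0289 and 0.0502 per month.
- Proportion with observed local failure by 24 months: F = [hL/(hL + hD)] × [1 − exp(−24(hL + hD))].
- Crude control = 1 − F.
- Alive and locally controlled at 24 months = exp(−24(hL + hD)) = 0.60 × (1 − mortality).

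**Results.**

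| 24-month mortality | hL/(hL+hD) | 1 − exp(…) | F | Crude control | Alive and locally controlled |
|---|---|---|---|---|---|
| 30% | 0.589 | 0.58 | 0.342 | 66% | 42% |
| 50% | 0.424 | 0.70 | 0.297 | 70% | 30% |
| 70% | 0.298 | 0.82 | 0.244 | 76% | 18% |

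The local-failure hazard is the same in every row. Crude control rises with mortality, while the proportion alive and locally controlled falls. The gap between the last two columns is deaths without local failure: about 24%, 40% and 58% of patients.

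**Other local-failure rates.** With net local failure of 20%, 30% or 40% in both arms, and mortality of 20% vs 50%, 30% vs 60% or 40% vs 70%, the higher-mortality arm shows crude control 3.4 to 7.6 points higher. At 30% local failure and 30% vs 60% mortality it is 74.5% vs 79.8%, against 49% vs 28% alive and locally controlled.

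**Loss to follow-up.** Add a dropout hazard of 20% at 24 months (assumed), −ln(0.80)/24 = 0.0093, at 50% mortality. F becomes 0.358 × 0.76 = 0.272, so crude control moves from 70% to 73%.

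**Time point.** At 50% mortality without dropout, crude control is 89% at 6 months, 81% at 12 and 70% at 24.

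**Size in patients.** From 30% to 70% mortality, crude control rises by 0.342 − 0.244 = 0.098. Over 12 patients that is about 1.2 patients. The exact 95% interval for 9 of 12 is 43% to 95%.

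**What a competing-risks analysis would show.** F is itself the cumulative incidence of local failure with death competing. With complete follow-up, an Aalen-Johansen estimate at 24 months equals the crude failure proportion, and Gray's test compares those same curves. That approach corrects for loss and fixes the time point, but the arm with more deaths still looks better.

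**The case against.** The strongest reply is that the plan nowhere says deaths and losses count as controlled. That is correct. A reader might infer that it does, but the text gives no rule; if deaths were coded as failures, the direction would change. What stands is that the default coding gives the bias described and nothing in the plan excludes it.

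A reader might also infer that incomplete follow-up is built into the design. It is not. Each patient has a planned 24 months, and the study duration allows for this after recruitment, so short observation would come mainly from death, loss or withdrawal. Section 5.8 requires active tracing before a patient is declared lost, and the 20% dropout above is an assumption. Adding a 24-month time point would settle part of the problem, but not the handling of deaths.

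Nor does the different treatment of DMFS make the plan contradict itself. DMFS is a composite with death built in and local control is listed as a rate, so different methods are permissible. The contrast shows only that a suitable method is already in the section. OS and DMFS will be reported alongside, so a mortality imbalance would be visible, though the local control comparison would not be corrected for it.

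Finally, the effect is small against sampling error at this size. That stands and limits the weight of the point.

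**Conclusion.** The concern holds in a limited form. The planned method for local control cannot handle death or loss to follow-up and has no time point. On the default reading it favours the arm with higher mortality: by 3.4 to 7.6 points for mortality differences of 30 percentage points, and by about 10 points for 30% against 70% mortality. These figures rest on assumed rates and constant independent hazards. The direction rests on deaths being coded as controlled, which is inferred.

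A reader might conclude that the trial's main result is at risk. The documents do not support that: local control is exploratory, the sample size rests on the primary endpoint alone, and the shift is around one patient per arm. Margin negative resection, fixed at surgery, is not affected. The change is still worth making, because it is cheap and removes a post hoc choice about how deaths are coded.

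**What to change.** In Section 13.4.4, replace the binomial analysis of local control with local-failure-free survival:

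- Time from treatment to local failure or death, whichever is first, with other patients censored at last follow-up, in parallel with DMFS.
- Kaplan-Meier estimates at 12 and 24 months, and a log-rank comparison of the arms.
- A definition of local failure, stating what counts in unresected patients, whom Section 5.3 keeps evaluable.

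If cumulative incidence of local failure is also reported, show it beside the incidence of death without local failure and compare arms with a cause-specific log-rank test. Aalen-Johansen with Gray's test alone does not remove the effect of mortality. Keep the binomial interval and the chi-square or Fisher test for margin status.

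The cost is SAP wording and slightly more analysis work in SAS. The follow-up, progression and death forms are already scheduled in Section 10; confirm that the progression form separates local from distant failure. The trade-off is that the endpoint becomes a composite with death, so it no longer describes local failure alone.
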